9. Subjects involved in litigation regarding injury or worker's compensation benefits.	9. History, self-report
10. Subjects with a diagnosis of vasculitis, peripheral vascular disease, peripheral neuropathy, small-fiber neuropathy, or fibromyalgia.	10. Medical history, self-report.

Subject Screening:

Subjects will be referred to the study from the Addiction Institute Opioid Treatment Program. Subjects will also be recruited by word of mouth, fliers, newspaper advertisements, and postings on relevant websites. Contact information will be provided so that potential subjects may speak with a research coordinator/research assistant to learn more about the opportunity to participate in the study. Potential participants will take part in a brief phone interview to establish pre-eligibility. Pre-eligible participants will be given an appointment for a screening visit.

They will then undergo additional screening for the study, including a SCID, review of metal implants, pregnancy test (if indicated), medical history, physical exam, vital signs (HR, BP, temp), TASS, and consent for study procedures. For all females of child-bearing potential, a pregnancy test will be repeated prior to beginning rTMS sessions. Daily medication use will be assessed for the 4 weeks prior to study entry using the time-line follow back procedure.

Following screening, the subjects will undergo the following procedures:

- 1) Pregnancy tests will be performed weekly during rTMS and before each MRI. Before the rTMS begins, we will perform an initial determination of motor threshold. Subjects with a motor threshold of 85% (of maximal stimulator output) at the initial determination of motor threshold will be removed from the study. The rationale for this is that, in our experience, high motor thresholds of this level result in discomfort and anxiety when the actual rTMS sessions are delivered.
- 2) Volumetric MRI and MRS scans.
- 3) Baseline neuropsychological testing, including pain scales.
- 4) Five weeks of rTMS, Monday – Friday, on an outpatient basis. The pain scales will be performed during the weeks of rTMS, up to daily.
- 5) Repeat volumetric MRI and MRS scans after the rTMS.
- 6) Repeat neuropsychological tests after the rTMS.

Neuropsychological scales and tests: Subjects will be asked to complete the following tests and scales before and after the sessions of rTMS (at baseline and after the completion of the rTMS).

Scales (expected to take 60 minutes total):

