1. Brief Pain Inventory (at baseline and daily before each rTMS session)
2. PEG scale (at baseline and weekly before each rTMS session)
3. PROMIS-29 pain intensity and pain interference items (at baseline and weekly before each rTMS session)
4. Hamilton Depression Rating Scale (at baseline and weekly)
5. Barratt Impulsiveness Scale (BIS -11) (at baseline)
6. Columbia Suicide Severity Rating Scale (at baseline and weekly)
7. Young Mania Rating Scales (at baseline and weekly)
8. Patient-rated clinical global impression (CGI) scale (at baseline and weekly)
9. Clinician-rated CGI scale (at baseline and weekly)
10. Clinician-rated CGI-opioid scale (at baseline and weekly)
11. Clinical Opiate Withdrawal Scale (COWS) (at baseline and weekly)
12. Quality of Life Enjoyment and Satisfaction Questionnaire (Q-LES-Q) (at baseline and weekly)

Medication use: Subjects will be asked to provide to us the number of medications they took as follows: 1) at baseline (in the week prior to starting sessions); and 2) at each session, where we will ask about opioid and other medication use since the previous session. The amount of opioids used will be converted to oral morphine equivalents and tallied for each day.

Repetitive Transcranial Magentic Stimulation (rTMS): The participants will be randomized into 2 groups: 1) high frequency rTMS (20 Hz), 2) and sham treatment. The rTMS will be administered using the TMS system provided by Brainsway (Brainsway, LTD, Jerusalem, Israel). The rTMS system is equipped with a positioning and cooling system. The positioning system includes a helmet that comprises the coils (which will be either the sham or the H coil), an adjustable arm connected to the helmet, and a device enabling rotation of the helmet around three orthogonal rotation axes. The positioning device enables the accurate and comfortable placement of the coil over the patient's head. The cooling system is designed to maintain ambient temperature in the coils during repetitive operation by allowing streamed the cooled air into the helmet and maintains the coils at ambient temperature.

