Motor threshold determination: In order to determine the resting motor threshold (RMT), subjects will be seated in a recliner with hands in a comfortable resting position and wearing the helmet which holds the H coil tangentially to the skull surface. TMS pulses will be applied over the leg motor area to induce activation of the tibialis. The optimal site for stimulation of the right tibialis muscle will be determined. The optimal stimulation site is defined as the position from which the largest motor-evoked potentials (MEPs) were consistently obtained. RMT is identified as the lowest stimulus intensity (in percentage of maximum stimulator output) that elicited at least five small MEPs (greater than 50 μ V) out of 10 consecutive stimulations. The first determination of the RMT can take up to 15-30 minutes. To help decrease risk of seizure, subjects will have their motor threshold determined once at the start of each week of rTMS and 100 - 110% of that stimulus intensity will be used for treatment of the anterior cingulate cortex, by positioning the coil over the midline, 5cm anterior to the optimal site for stimulation of the tibialis. We will begin with an intensity of 80% and increase to 110% over 2-3 days.

Sham method: A sham coil is placed in the helmet along with the active coil. The determination of the operating mode (active or sham) is done using magnetic cards. The sham coil setting is designed to mimic the auditory artifact and the scalp sensations evoked by the real coil, and to produce activation of facial muscles similar to the effect of a real H coil, without stimulating the brain itself.

Stimulation procedure: A pre-selected treatment protocol will be programmed into the rTMS stimulator. The stimulator sends electrical pulses to the coil positioned (within the helmet) on the subject's scalp at the intended site of stimulation (approximately 5cm downward from positioning at motor threshold determination, along the midline). Magnetic field intensity is set at 110% of that subject's observed RMT. rTMS will be delivered as shown:

Active rTMS (H coil)

Amplitude (% motor threshold)	80-110%
Frequency (pulses per second, Hz)	20 Hz
Train Duration (seconds)	2 s
# pulses / train	40
Time between trains (seconds)	20 s
Number of trains/session	50
Total number of pulses/session	2000

The rTMS will be administered at the STARS outpatient research clinic.

The staff members who will administer the rTMS will be required to meet all of the following:

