The effect of rTMS on chronic pain will be performed with a repeated measure ANOVA. Post-hoc contrasts between the groups will be assessed with t tests with correction for multiple comparisons. Groups will be prospectively matched for variables suspected to influence the outcome measures (age, gender, ethnicity). The effect of these variables on each dependent variable will be assessed by ANOVA. In case of significant or near significant effect ($p < 0.10$), these variables will be included in the model (ANCOVA). For all analyses described above, a two tailed probability value of $p < 0.05$ will be selected as significance threshold and correction for multiple comparisons will be applied. In case of nonnormality or inhomogeneity of variance, we will first evaluate data transformation techniques (log or square root) to address these issues. If this cannot be achieved, we will use nonparametric tests, or bootstrap analysis.

Criteria for Early Discontinuation

Subjects will be assessed at least weekly by a study psychiatrist. Subjects will be removed from the study if they experience a worsening of depressive symptoms or an HRSD > 17 . Any answer of “yes” on the Columbia Suicide Severity Rating Scale or a score of > 10 on the Young Mania Scale will require a psychiatric evaluation to determine if continuation in the study is appropriate.

A Clinical Global Impression-improvement score and CGI opioid improvement score will be obtained weekly by a study physician. Subjects will be assessed, by a study physician, for continuation in the study if they score 6 or 7.

Risks associated with the study:

1. MRI scans.

The scan may be dangerous if combined with magnetic objects in the body. While there have been no reports of any harmful long-term effects caused by the MRI scanner, including magnets of high strength, the long-term effects of being placed in a magnet of the strength used in this study is unknown. Subjects with metallic objects in their body which would exclude them from receiving an MRI for clinical purposes are excluded from the

study. Also, although there are no known risks associated with pregnancy, subjects will not be included if pregnant.

2. Reduction in opioid use.

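### Allocation is described both as randomisation and as prospective matching, with no stated concealment or timing, and the matched factors are modelled only if p<0.10

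*Combined protocol and SAP*

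**What the plan says.** The only account of randomisation is one sentence in the section Repetitive Transcranial Magnetic Stimulation: "The participants will be randomized into 2 groups: 1) high frequency rTMS (20 Hz), 2) and sham treatment". It gives no ratio, sequence generation, blocking or stratification.

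Statistical Analysis then states: "Groups will be prospectively matched for variables suspected to influence the outcome measures (age, gender, ethnicity". It gives no categories, tolerances or procedure for the matching. The same paragraph tests whether each of these variables affects each outcome and continues: "In case of significant or near significant effect ($p < 0.10$), these variables will be included in the model (ANCOVA".

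Under Subject Screening, a numbered list opens with "Following screening, the subjects will undergo the following procedures". Its six items are pregnancy tests and motor threshold, MRI/MRS, baseline tests with pain scales, five weeks of rTMS, repeat scans and repeat tests. Allocation is not among them. Item 1 contains a removal rule: "Subjects with a motor threshold of 85% (of maximal stimulator output) at the initial determination of motor threshold will be removed from the study".

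Under Sham method, the arm is delivered as follows: "The determination of the operating mode (active or sham) is done using magnetic cards". The protocol does not say who prepares, holds or issues the cards, or whether they are coded.

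**The concern.** Randomising individuals and matching groups as subjects arrive are different instructions unless a procedure joins them, such as stratified randomisation, minimisation, or randomisation within pairs. The protocol names none. One site could use simple randomisation and ignore the matching sentence. Another could compare each arrival with those already in each arm and place that person to keep balance. Both could point to the text, yet the second need not involve chance at all.

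If the next arm can be foreseen, the decision to enrol, delay or remove a subject can depend on it. The group comparisons in Statistical Analysis rely on random assignment, and selection of this kind cannot be undone in the analysis. The undefined timing adds to the problem. If the arm is known before the threshold check, the first scan or the baseline scales, losses and ratings at those steps could differ by arm.

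The modelling rule raises a smaller, separate issue. Factors used to form the groups belong in the analysis by design. Here each is kept or dropped on a significance test, outcome by outcome.

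**Working it through.** The plan states no figure on this point, so there is nothing to reproduce. The main check sets the sections side by side.

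1. **Method.** The rTMS section randomises and Statistical Analysis matches prospectively. No section mentions strata, blocks, minimisation or pairs, so the two statements are compatible only if the reader supplies the link.
2. **Concealment.** Mode is set by magnetic card. Custody and coding of the cards are not described. The sham features ("The sham coil setting is designed to mimic the auditory artifact and the scalp sensations evoked by the real coil") support masking of the participant during treatment. They say nothing about who can see the next assignment.
3. **Timing.** Items 1 to 3 of the numbered list come before treatment, and item 1 can remove a subject. No sentence places allocation before or after any of them. The staff requirements ask those who administer rTMS to be able to determine the motor threshold, so the person measuring the removal criterion may also be the person who handles the card.
4. **Analysis.** Age, gender and ethnicity are matched by design but modelled only at p<0.10. In a small trial, a factor that matters can miss that cut-off. The chosen model can also differ between outcomes.

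**Illustration only.** How far matching could expose the next arm depends on its meaning and on whether staff see past allocations. Assumptions, none of them from the protocol: 2 age × 2 gender × 3 ethnicity categories = 12 equally likely cells, 1:1 allocation, total N of 10 to 40, and staff who know all earlier arms. Simulated share of correct guesses (4,000 trials per setting):

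| N | Simple randomisation | Pairs within cell | Deterministic minimisation | Minimisation, 0.8 random element |
|---|---|---|---|---|
| 10 | 0.498 | 0.625 | 0.854 | 0.722 |
| 20 | 0.501 | 0.674 | 0.877 | 0.739 |
| 30 | 0.500 | 0.700 | 0.885 | 0.744 |
| 40 | 0.499 | 0.713 | 0.888 | 0.750 |

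The pairs column can be checked by hand. Arrival i finds an unpaired member in the same cell with probability (1 − (5/6)^(i−1))/2. The average over i = 1 to N is d, the share of assignments fully determined, and the guess rate is d + (1 − d)/2.

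- N = 10: the sum of (5/6)^(i−1) is 6 × (1 − 0.1615) = 5.031. So d = (1 − 5.031/10)/2 = 0.248, and the guess rate is 0.248 + 0.752/2 = 0.624.
- N = 40: the sum is 6 × (1 − 0.0007) = 5.996. So d = (1 − 5.996/40)/2 = 0.425, and the guess rate is 0.425 + 0.575/2 = 0.713.

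Both agree with the simulation. The guess rate runs from 50% to 89% across readings of the text, which is why no single figure can be attached to this protocol.

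**The case against.** The strongest reply is that the protocol does say randomised, and that matching may be loose wording for stratification or minimisation. The matching sentence sits in the analysis section and leads straight into covariate handling. Stratified lists or an off-site allocator would satisfy it without anyone at the site seeing a running tally. This is a fair reading, and it rules out treating the two sentences as a proven contradiction. It does not supply the missing procedure.

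On timing, the numbered list covers what subjects undergo, and allocation is an administrative act. The card is first needed at item 4, and the threshold is a measured quantity (at least five of 10 responses above 50 μV). All of this makes late allocation plausible and limits discretion, but no sentence requires late allocation.

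On the remedy, minimisation with a 0.8 random element is guessed 72% to 75% of the time in the illustration, against 63% to 71% for pairing. This stands. A random element alone does not protect the trial if staff see past arms. Independent custody of the sequence does most of the work.

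Finally, the Introductory statement calls this a feasibility study, and Specific Aim 1 treats the pain effect as exploratory. That lowers the stakes without removing them. The same aim hypothesises that active beats sham, a primary effectiveness outcome is named, and the groups are tested at two-sided p<0.05.

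**Conclusion.** The concern holds as a gap in specification that should be fixed. Randomisation and prospective matching are not reconciled, concealment is not described, allocation has no stated place relative to the 85% motor-threshold removal, the baseline scans and the baseline scales, and the matched factors may be left out of the model. Foreseeable allocation and removals after allocation therefore cannot be ruled out.

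A reader might infer three stronger claims, and the documents support none of them:

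- **That staff can foresee or steer allocation.** This would require staff to know earlier arms and to see or control the next one. The protocol is silent on both.
- **That half of all assignments, or even all of them, are known in advance.** The protocol never mentions pairs. Half is a ceiling that is reached only if every subject finds a match and earlier arms are visible. In the illustration the share determined is 25% to 43%. Full predictability would require exact balance to be enforced by hand.
- **That baseline ratings are unblinded.** Rater blinding is not described either way.

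No size of bias can be derived from the protocol. The illustrative figures rest entirely on the assumptions listed with them.

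**What to change.** 1. Replace the matching sentence in Statistical Analysis with one named method that contains a random element. Examples are 1:1 stratified permuted blocks of undisclosed, varying size with few strata, or minimisation with a random element. State the ratio and the factors. With three candidate factors and no stated sample size, few strata or minimisation is safer than a full cross-classification.
2. State that the sequence and the coded mode cards are prepared and held by someone who does not recruit, treat or rate.
3. Add a step between items 3 and 4 of the numbered list under Subject Screening: allocate only after the motor-threshold check, baseline MRI/MRS and baseline scales are complete, and release the card code after that point.
4. Drop the p<0.10 rule for the balancing factors and include them in every outcome model.

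The cost is one replaced sentence, one custody sentence, one added step and one changed modelling rule, plus a randomisation list. The downside is slightly looser balance on age, gender and ethnicity than exact matching would give. Fixed factors also use a few degrees of freedom, which is another reason to keep them few. The change has to be in place before the first subject is allocated.

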Specific Aim 1: Investigate the feasibility and tolerability of using rTMS on chronic pain in patients with opioid use disorder currently on methadone maintenance therapy and to investigate the effect of rTMS on chronic pain relief and substance use in an exploratory manner. Previous studies indicate that deep brain stimulation of the prefrontal cortex/anterior cingulate induces pain relief. Our hypothesis is that active rTMS, compared to sham, will improve pain after five weeks of treatment, thereby improving functional capacity and reducing opioid and other substance use.

Specific Aim 2: Investigation of the effect of rTMS using imaging. We will investigate target engagement with brain imaging. Magnetic resonance spectroscopy (MRS) will be used to measure changes in glutamate and vMRI to gauge changes in volume. Our hypothesis is that active rTMS will decrease glutamate levels and increase brain volume of the mPFC and ACC compared to sham.

Specific Aim 3: Investigation of the effect of rTMS on cognitive (i.e. executive) functioning in patients with chronic pain and opioid use disorder on methadone maintenance therapy. Previous studies have implicated a broad range of cognitive deficits in patients with substance use disorders, both during intoxication and withdrawal and after prolonged abstinence. Neuropsychological testing completed before and after rTMS treatment will be completed to determine if rTMS improves cognitive functioning, which may be a possible mechanism for improvement in chronic pain and/or opioid use disorder.

Background and Rational

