- Practical demonstration of ability to perform several determinations (at least 5) of the resting motor threshold, under the direct supervision of a physician investigator experienced in rTMS.
- Performing at least the first two rTMS study sessions under the direct supervision of a physician investigator experienced in rTMS.
- Working knowledge of the principles and practices of rTMS and the rTMS device being used in the study, including common side-effects and how to recognize them. Knowledge will be based on completed tutorial sessions with the investigators or rTMS consultant experienced in rTMS.
- Knowledge how to contact the covering physician available in the building.
- Knowledge of seizure first aid, the location of the emergency equipment and medication, how to engage the emergency response system.
- Bachelor's degree or higher.

In addition, a physician with the following qualifications will be readily available in the vicinity if the need arises (in the institute, and immediately available).

Post-treatment Follow-up

Participants will return at 2 weeks and 4 weeks after completion of rTMS for the following measures:

1. Self-reported methadone dose adjustments/changes and other substance use

2. Brief Pain Inventory
3. PEG scale
4. PROMIS-29 pain intensity and pain interference items
5. Hamilton Depression Rating Scale
6. Hamilton Anxiety Rating Scale
7. Patient-rated clinical global impression (CGI) scale
8. Clinician-rated CGI scale
9. Clinician-rated CGI-opioid scale
10. Quality of Life Enjoyment and Satisfaction Questionnaire
11. Visual Analogue Scale (VAS) for Opioid Craving

Statistical Analysis:

The primary effectiveness outcome measure will be proportion of subjects who achieve $\geq 50\%$ reduction in average pain score as measured by VAS and no significant increase in opioid medication use [defined as greater than 25% increase in morphine equivalent dose].

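### The exploratory continuous pain analysis gives baseline pain no stated role, names no tested term or visit, and screens covariates at p<0.10; one short pre-specified baseline-adjusted model would usually be more precise

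*Combined protocol and SAP*

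**What the plan says.** The Statistical Analysis section covers continuous pain in one sentence: "The effect of rTMS on chronic pain will be performed with a repeated measure ANOVA". Next come post-hoc t tests between the groups with a multiplicity correction, without a visit or a scale (raw score or change).

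On covariates it says: "Groups will be prospectively matched for variables suspected to influence the outcome measures (age, gender, ethnicity"). It continues: "The effect of these variables on each dependent variable will be assessed by ANOVA". Where the effect reaches p<0.10, "these variables will be included in the model (ANCOVA"). The candidates are therefore named in advance, but their entry is decided outcome by outcome from the trial data. Baseline pain is not a candidate.

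Two other places bear on this:

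- Specific Aim 1 calls the investigation of pain relief exploratory, and ties the hypothesis to a time: "active rTMS, compared to sham, will improve pain after five weeks of treatment".
- The scale list under Neuropsychological scales and tests provides baseline values: "Brief Pain Inventory (at baseline and daily before each rTMS session") and "PEG scale (at baseline and weekly before each rTMS session"). The PROMIS-29 pain items follow the PEG schedule.

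The primary effectiveness outcome is separate. It is a binary responder proportion combining a 50% "reduction in average pain score as measured by VAS" with a limit on the increase in opioid use.

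**The concern.** Baseline could be a covariate, a level of the time factor, subtracted from follow-up, or left out. The tested term could be the group main effect or group-by-time, and the t tests could be at any visit. These choices estimate different quantities with different power. Left open, they can be settled after the data are seen, in an analysis that applies a two-sided 0.05 threshold.

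The p<0.10 rule adds a second data-dependent step. The covariate set can differ between outcomes, and the plan does not say whether arm is in the screening test. At stake are precision and a single unambiguous estimate in what is likely to be a small trial.

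**Working it through.** **Inputs.** From the documents: two randomised arms, two-sided 5%, baseline plus weekly (PEG, PROMIS) or daily (BPI) pain scores, five weeks of treatment, three candidate covariates. Not in the documents, so assumed: 1:1 allocation, n = 10 or 20 per arm, a true difference d = 0.8 SD at week 5, and correlation r = 0.3 to 0.7 between scores. The plan states no power or sample size to reproduce.

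**1. Single week-5 endpoint.** Write the variance of the arm difference as (2/n)·V, in SD² units:

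- follow-up only: V = 1
- change score: V = 2(1−r)
- baseline ANCOVA: V = (1−r²)·[1 + 1/(2n−4)]

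Power comes from the noncentral F with λ = n·d²/(2V), on 1 and 2n−2 df (2n−3 for ANCOVA). At r = 0.5 and n = 10, V is 1, 1 and 0.75 × 1.0625 = 0.797, so λ = 3.2, 3.2 and 4.02. At n = 20 the ANCOVA V is 0.75 × 1.0278 = 0.771, so λ = 6.4, 6.4 and 8.30.

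| Power %, 10 / 20 per arm | r = 0.3 | r = 0.5 | r = 0.7 |
|---|---|---|---|
| Follow-up only | 40 / 69 | 40 / 69 | 40 / 69 |
| Change score | 30 / 55 | 40 / 69 | 59 / 89 |
| Baseline ANCOVA | 40 / 72 | 47 / 80 | 63 / 93 |

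**2. Repeated measures readings.** Take baseline plus five weekly scores (K = 6), equal correlations, and arm effects e at each occasion.

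*Group-by-time:* λ = n·Σ(e−ē)²/[2(1−r)], on 5 and 5(2n−2) df. An effect constant from week 1 has Σ = 0.533; one building linearly to week 5 has Σ = 0.448. At r = 0.5, λ = 5.33 / 10.67 and 4.48 / 8.96, giving power 36 / 70 and 31 / 61.

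*Group main effect with baseline as a level of time:* the variance per patient mean is (1+5r)/6 = 0.583 at r = 0.5, and the mean effect is 0.667 (constant) or 0.40 (building). Power is 46 / 77 or 20 / 36. Much therefore depends on an unnamed term.

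*Where week-5 ANCOVA loses:*

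- r = 0.3, constant effect: main effect 59 / 89 against 40 / 72.
- r = 0.8, constant effect: group-by-time 79 / 99 against 78 / 98.
- Correlation decaying with lag, immediate effect, r = 0.7 (6,000 simulated trials): group-by-time 69 / 98 against 62 / 93.

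**3. Cost of adjustment.** If baseline is uninformative, the variance rises by 1/(N−4) for total N:

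- N = 10: 16.7%
- N = 12: 12.5%
- N = 20: 6.25%
- N = 40: 2.8%

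Now add three non-prognostic one-df factors that are only loosely balanced. The variance factor becomes 1 + 4/(2n−7), with 2n−6 df. At 10 per arm and r = 0.3 / 0.5 / 0.7, power is 33 / 39 / 53, against 40 / 40 / 59 for the better of follow-up only and change score. At 20 per arm it is 68 / 76 / 90 against 69 / 69 / 89. Simulation at 10 per arm and r = 0.5 agrees: 48.0% with baseline alone, 40.5% with the three null factors added. Conversely, omitting strong factors (R² = 0.10 each) costs power: 43.7% without them against 52.9% with them at 10 per arm, and 76.7% against 89.4% at 20.

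**4. The screen.** With three independent null covariates, at least one passes p<0.10 in about 1 − 0.9³ = 27% of trials. Simulated effects, with true difference 0.80 SD and 30,000 trials per cell:

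| Screening setting | Mean estimate, 10 / 20 per arm | Type I error, 10 / 20 per arm |
|---|---|---|
| Unmatched, arm not in screening test | 0.73-0.77 / 0.76-0.78 | 4.9-5.1% overall |
| Unmatched, arm in screening test | no shift | 6.3-7.2% / 5.6-6.0% |
| Exactly matched, either way | no shift | 4.5-5.7% overall |

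With exact matching and r = 0.5, replacing the screened model without baseline by fixed factors plus baseline raised power from 41.3, 42.8 and 50.1 to 46.0, 48.8 and 60.4 at 10 per arm, for factor R² of 0, 0.02 and 0.10.

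**The case against.** This is a feasibility study, the pain analysis is exploratory, and every power above rests on assumed inputs. The covariates are named in advance, and the post-hoc t tests do give a between-group comparison. A repeated measures ANOVA may also carry baseline implicitly as a time level. The baseline-adjusted model does not always win: step 2 shows reversals, and step 3 shows that a longer covariate list can erase the gain at 10 per arm.

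Most of this stands and limits the point. It does not remove it. The t tests have no visit or scale, and an implicit baseline level would still leave the tested term open. Exploratory status lowers the stakes, but the section sets a formal significance threshold.

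A reader might infer that the screen materially biases the estimate or inflates type I error. The documents do not support that: the section plans matching on these same three variables, and with close matching both effects largely disappear. How close the matching will be is not stated, since the treatment section says only that participants are randomised. A reader might also infer that baseline adjustment is almost free. That is fair for baseline alone from about 20 patients in total. It is not fair at 10 to 12 patients, nor for baseline plus several uninformative factors.

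**Conclusion.** The point holds as an under-specified exploratory analysis with an inexpensive improvement. At r = 0.5, baseline ANCOVA gains about 7 points of power at 10 per arm (47.2 − 39.5 = 7.7) and about 11 at 20 per arm (80.1 − 69.3 = 10.8) over a change score or follow-up-only test. Over group-by-time with equal correlations it gains about 11 to 16 and 10 to 19 points.

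These sizes depend on the assumed effect, sample size, correlation and time course. Group-by-time, or a main effect over all visits, can do better for early constant effects, high correlation or decaying correlation. That is a reason to name the contrast in advance, not to leave it open.

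The harm from the screen is minor and conditional. The binary primary outcome follows its own definition, and nothing here shows that it is compromised. The change is worth making but does not threaten the trial's main conclusion.

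**What to change.** For continuous outcomes only:

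- Delete the p<0.10 rule.
- Pre-specify one model with arm, the outcome's own baseline value as a covariate (not a level of time), and a short fixed list limited to factors actually used to balance allocation. Keep these whatever their p-values.
- State which of age, gender and ethnicity are used in allocation. If another factor is expected to be strongly prognostic, name it now.
- Name the pain score and one primary contrast. The arm difference at week 5 fits Specific Aim 1; if the daily BPI is used, take the mean of the week-5 scores. State what the post-hoc t tests add.

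The cost is a few sentences and no new data, because the BPI, PEG and PROMIS pain items are already taken at baseline. Statistically it is one degree of freedom for baseline: about 6% of variance or less from about 20 patients in total, but 12-17% at 10 to 12 patients if baseline is uninformative. Each further loosely balanced null factor costs more, which is why the list must stay short.
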